#### The SAS sample code is listed:

```
*****************
 TREATMENT: 0 (Placebo), 1 (CIVI 007 comma Q4W x2),
           2 (CIVI 007 _{
m co} mg on Day 1 followed by _{
m co} mg on Day 29), or
           3 (CIVI 007 cc mg Q4W x2)
 BASE: Baseline PCSK9 or LDL-C
 CHG: Change from baseline to the specified visit in PCSK9 or LDL-C
************************
proc glm;
 class TREATMENT;
 model CHG = TREATMENT BASE / p;
 lsmeans TREATMENT / stderr pdiff cl;
 estimate "CIVI 007 cm mg Q4W x2: Placebo" TREATMENT -1 0 0 1;
 estimate "CIVI 007 co mg on Day 1 followed by co mg on Day 29: Placebo"
         TREATMENT \overline{-1} 0 1 0;
 estimate "CIVI 007 comma Q4W x2: Placebo" TREATMENT -1 1 0 0;
run;
```

The treatment comparisons between each active dose versus placebo will be tested following a fixed sequence step-down procedure to control the multiplicity.

Analysis of the secondary efficacy endpoints will be repeated with the PP Population.

Mixed-Effect Model Repeated Measure (MMRM) method may be used to test the robustness of the results with baseline value, treatment and visit as factors, and treatment by visit interaction. An unstructured covariance matrix will be used (TYPE=UN). The treatment difference will be estimated from the MMRM. No imputation will be performed. The SAS sample code is listed:

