9.2.2.1 Secondary efficacy analysis

The secondary endpoints of the study will be analyzed using analysis of covariance (ANCOVA) models to compare the mean percent change from baseline in LDL-C and PCSK9 28 days after the first injection and 28 and 56 days after the second injection of study drug between treatment

groups with placebo. This ANCOVA model will include treatment as a factor and baseline level as a covariate.

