#### 2.3.2 Secondary Endpoints

The secondary efficacy endpoints include the following changes from baseline measured approximately 28 days after the first and 28 and 56 days after the last injection of study drug:

The percent change in PCSK9 and LDL-C

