# 3.4.1 Secondary Efficacy Endpoints Analyses

The PCSK9 and LDL-C will be listed and summarized using descriptive statistics by treatment group over the study period to describe absolute and percent changes from baseline.

The secondary endpoints of the study will be analyzed using analysis of covariance (ANCOVA) models to compare the mean percent change from baseline in LDL-C and PCSK9 approximately 28 days after the first injection (Day 29) and approximately 28 and 56 days after the second injection of study drug (Day 57 and Day 85) between treatment groups with placebo. This ANCOVA model will include treatment as a factor and baseline level as a covariate. The missing values will be imputed by last observation carried forward (LOCF) method.

Normality will be tested for the model residuals and the p-value from the Shapiro-Wilk test will be provided. If the residuals of this model are not normal, then non-parametric analyses (Wilcoxon rank- sum test) will be explored to compare the difference in median percent change between treatment groups.

The presentation of results will be the observed data and include the estimated means by treatment group, their standard errors, and the estimated differences in means between the patient treatments and corresponding 95% confidence intervals and p-values.

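### SAP 3.4.1 sample code does not say that the secondary ANCOVA response is percent change, and SAP 3.4.2 attaches a log to a percent change without naming a quantity that can be logged

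*SAP*

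**What the plan says.** **Secondary response, in the text.** SAP 2.3.2 gives the secondary endpoint as "The percent change in PCSK9 and LDL-C", and Protocol 7.2 has the same endpoint. SAP 3.4.1 says that the ANCOVA will "compare the mean percent change from baseline in LDL-C and PCSK9 approximately 28 days after the first injection", and likewise at Days 57 and 85. Protocol 9.2.2.1 agrees: "compare the mean percent change from baseline in LDL-C and PCSK9 28 days after the first injection". If residuals are not normal, the Wilcoxon test "will be explored to compare the difference in median percent change between treatment groups". The promised output is "the estimated differences in means between the patient treatments and corresponding 95% confidence intervals and p-values".

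**Secondary response, in the code.** The block in SAP 3.4.1 defines "CHG: Change from baseline to the specified visit in PCSK9 or LDL-C" and fits "model CHG = TREATMENT BASE / p". It defines no percent-change variable.

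**Exploratory endpoints.** SAP 2.3.3.1 lists PCSK9 and LDL-C as absolute change only, and most other lipids as both absolute and percent change. SAP 3.4.2 reuses the secondary ANCOVA for these without naming the response for each one. It adds that for some endpoints, with percent change in triglycerides as its example, a log transformation may precede the model. It gives no ratio form, offset or back-transformation.

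**The concern.** Two instructions do not lead unambiguously to the analysis intended.

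1. A programmer who fills CHG with value minus baseline would report a difference in concentration units where the plan promises a difference in mean percent change. That result belongs to the exploratory tier. The p-values feed the fixed-sequence comparisons in 3.4.1, so the scale should not be left to interpretation.
2. A log applied to percent change drops every patient whose triglycerides fell or stayed level. Patients would then be excluded according to their response, and by arm if treatment affects triglycerides.

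Both points concern secondary or exploratory endpoints. The primary objective is safety, so the stakes are limited.

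**Working it through.** The documents give no effect size, SD or power figure, so there is no stated number to reproduce. The steps below show that the readings differ, and by how much under labelled assumptions.

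**Step 1. The two scales.** Document inputs: LDL-C entry thresholds of 70 and 100 mg/dL (Protocol 4.1) and 12 patients per arm (SAP 2.2.4). Assumption: every active patient falls by 50% and placebo does not change, with no noise. Arms have the same mix of baselines, so the ANCOVA contrast equals the raw difference in means: -50 points for percent change, and -0.50 x mean baseline for absolute change.

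| Patients per arm at 70 / 100 | Mean baseline | Absolute contrast (mg/dL) | Percent contrast (points) |
|---|---|---|---|
| 12 / 0 | 70.0 | -35.00 | -50.0 |
| 9 / 3 | 77.5 | -38.75 | -50.0 |
| 6 / 6 | 85.0 | -42.50 | -50.0 |
| 3 / 9 | 92.5 | -46.25 | -50.0 |
| 0 / 12 | 100.0 | -50.00 | -50.0 |

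(With all baselines equal, the covariate is omitted.) Another assumed effect rescales the table. At -20% the absolute contrast runs from -14 to -20 mg/dL. The ratio of its ends is always 100/70 = 1.43.

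**Step 2. Would the scale change a significance call?** Simulation of the same model, 2,000 trials per effect, 12 per arm, effect in one active arm. All inputs are assumed: baseline LDL-C mean 115 and SD 30 mg/dL, floored at 70; SD of percent change 18.

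| True effect (points) | Mean estimate, percent scale | Mean estimate, absolute (mg/dL) | Trials with p-values on opposite sides of 0.05 |
|---|---|---|---|
| -10 | -10.1 | -11.6 | 5.7% |
| -15 | -15.0 | -17.3 | 7.2% |
| -20 | -20.1 | -23.3 | 6.4% |
| -50 | -50.3 | -58.1 | 0% |

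The estimate and its units change; the significance call seldom does.

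**Step 3. The log.** Let P be percent change. ln(P) exists only for P > 0, whereas ln(value/baseline) = ln(1 + P/100) exists for every positive measurement.

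| P | ln(P) | ln(1 + P/100) |
|---|---|---|
| -50 | undefined | -0.693 |
| -20 | undefined | -0.223 |
| 0 | undefined | 0 |
| +10 | 2.303 | 0.095 |
| +30 | 3.401 | 0.262 |

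Let q be the assumed share of patients without a rise. The expected number undefined is n x q, and the chance of at least one is 1 - (1 - q)^n.

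- q = 0.10: 1.2 of 12 and 4.8 of 48; chance 1 - 0.9^12 = 0.718 in one arm and 1 - 0.9^48 = 0.994 in the trial.
- q = 0.25: 3 of 12 and 12 of 48; chance 0.968 in one arm.
- q = 0.50 (median change zero): 6 of 12 and 24 of 48; chance 0.9998 in one arm.

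If percent change is instead assumed normal, with means from +10 to -20 and SDs from 20 to 40, q runs from 31% to 84%, or 3.7 to 10.1 patients of 12.

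**The case against.** The code comment does not say absolute. The endpoint definitions in Protocol 7.2 and SAP 2.3.2 use *changes from baseline* as an umbrella and then list percent change under it, and the protocol synopsis is equally loose. Where absolute change alone is meant, SAP 2.3.3.1 marks it. The text directly above the code names percent change, the block is a sample, and SAP 5 leaves detailed programming specifications to a separate document. On the log, SAP 3.4.2 names an endpoint and an optional step. Logging the triglyceride values, or their ratio to baseline, also fits the sentence.

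Much of this stands. A reader might infer that the code literally specifies the exploratory endpoint, or that the final secondary analysis will be on the wrong scale. The documents support neither: the comment is compatible with percent change, and the text governs. A reader might also infer that the analyst would be driven to choose a transformation after seeing the data. That does not follow, because it is known without data that a log needs a positive argument, and the form can be fixed before database lock.

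What does not fall away is that the code omits the one word that separates two endpoints the SAP keeps in different tiers, and that 3.4.2 names only a quantity whose log often does not exist. The programming specifications are not among the documents, so they cannot be taken to resolve either point.

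**Conclusion.** Both points hold as minor corrections. The code should state the response that the text already fixes, and 3.4.2 should name a quantity that can be logged.

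The size is modest. If CHG were coded as absolute change, the reported contrast would be in other units and would depend on the baseline mix (-35 to -50 mg/dL for one and the same 50% reduction). Under the simulation's assumptions, significance would differ in about 6 to 7% of trials for effects of -10 to -20 points and in none at -50. The log rule, applied to the quantity it names, would lose from about a tenth of values to more than half over the shares considered. The effect sizes, baseline distribution, SDs and shares without a rise are all illustrative assumptions, not document figures. The text mismatch and the domain of the log need no assumption.

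Nothing is concluded about the response in the MMRM code. SAP 3.4.1 announces it ("The treatment difference will be estimated from the MMRM. No imputation will be performed. The SAS sample code is listed"), but it is not visible in the text available for review.

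**What to change.** **SAP 3.4.1 code.** Define `PCHG = 100*(value - baseline)/baseline` and fit `model PCHG = TREATMENT BASE` for the secondary endpoints. Keep `CHG`, labelled as absolute change, for the exploratory absolute-change analyses. Check that the MMRM code uses the matching response.

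**SAP 3.4.2.** Name the response for each exploratory endpoint. Where a log is used, state that the response is log(value/baseline) with log(baseline) as covariate. Back-transform each arm's estimate m as 100*(exp(m) - 1), a geometric mean percent change, and report the treatment contrast as a ratio versus placebo. Other log forms would also be valid; what matters is that one is named before database lock.

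**Cost.** A few words and one variable, with no effect on data collection or sample size. The drawback is that contrasts for logged endpoints are relative, not differences in percentage points, and must be labelled so. With assumed arm results:

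- placebo +10%, active -20%: 0.80/1.10 = 0.727, so -27.3% relative against -30 points;
- placebo -10%, active -30%: 0.70/0.90 = 0.778, so -22.2% relative against -20 points;
- placebo 0%, active -20%: 0.80/1.00 = 0.800, so -20% on both.

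Where the arms differ, the two measures agree only when the placebo change is zero.

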## 3.4.2 Exploratory Efficacy Endpoints Analyses

The exploratory lipid/PD endpoints are listed in the section 2.3.3.1 excluding hsCRP. All the endpoints will be listed and summarized using descriptive statistics by treatment group over the study period to describe absolute and percent changes from baseline.

For continuous variables, the ANCOVA model specified for the secondary efficacy endpoints analysis will be used. The missing values will be imputed by LOCF method. For certain efficacy endpoints like the percent change in triglycerides, logarithmic transformation may be performed prior to fitting the ANCOVA model.

For certain efficacy endpoints, the MMRM method may be used to test the robustness of the results with baseline value, treatment and visit as factors, and treatment by visit interaction. An unstructured covariance matrix will be used (TYPE=UN). The treatment difference will be estimated from the MMRM. No imputation will be performed.

#### 3.5 Pharmacokinetic Assessment

Sparse PK sampling will be conducted for all consenting patients. Sampling will be performed on dosing days, and at each study visit during the Treatment and Follow-up Periods. For each of the dosing days, a PK sample will be drawn pre-dose (-1 hour), 3 hours (± 1 hour) post-dose, and at 8 hours (± 1 hour) post-dose.

The population PK model created based on data from the ongoing Phase 1 study will be refined to evaluate the relationship of CIVI 007 PK to demographics and background statin therapy. The model will be periodically refined as new and broader datasets emerge to include the covariates of special populations, concomitant medications, and disease state.

CiVi Biopharma, Inc. Protocol: CIVI 007-2-01

# 3.5.1 Handling Missing Data or Concentration Below the Lower Limit of Quantification

For non-compartmental analyses (NCA), missing or concentration below the lower limit of quantification (BLQ) data will be handled based on the current knowledge of the study drug.

If the actual sampling time is missing, but a valid concentration value has been measured, the concentration value will be flagged and the scheduled time point may be used for the calculation of PK parameters.

In cases of missing pre-dose values on Day 1, the missing components will be assumed as zero. In cases of a missing pre-dose value on Day 29, the individual minimum observed concentration during the dosing interval will be used as pre-dose concentration values. For the other cases, the missing data will not be imputed.

The following rules will be used to handle BLQ data for individual plot and PK parameter calculation:

- If BLQ values occur in a profile before the first measurable concentration, it is assigned as zero for Day 1 and as LLOQ for Day 29.
- If BLQ values occur between measurable concentrations or after the last measurable concentration, it is treated as missing.

The following rules will be used to handle BLQ data for mean plot and concentration summary:

- Mean concentration at any individual time point are only calculated if at least half (50%) of the patients have valid values (i.e., measurable and not missing) at this time point for each treatment.
- In cases where a mean value is not calculated due to the criterion above not met, the value will be set to missing
- BLQ will be set as zero. The only exception is that the pre-dose BLQ on Day 29 will be set as LLOQ
- Missing values are excluded from the calculation of these means.

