## 2.3.3.2 Pharmacokinetic (PK) Endpoints

The following PK parameters will be calculated for CIVI 007, where possible:

- Cmax
- time of the maximum observed plasma concentration (Tmax)
- AUC0-t
- concentration observed at pre-dose (Ctrough) (Day 29 only)

Additional exploratory PK parameters, which may include but are not limited to the following, may be calculated:

- area under the plasma concentration-time curve from time 0 extrapolated to infinity (AUC0-∞)
- area under the plasma concentration-time curve from time 0 to 168 hours (AUC0-168)

- percentage of AUC0-∞ that is due to extrapolation (%AUCextrap)
- apparent terminal elimination rate constant (λz)
- apparent plasma terminal elimination half-life (t1/2)
- apparent total plasma clearance (CL/F)
- apparent volume of distribution during the terminal phase (Vz/F)

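### SAP 3.5.1 puts an artificial value into the Day 29 trough: BLQ becomes LLOQ, and a missing value is filled from an unnamed dosing interval

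*SAP*

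**What the plan says.** SAP 3.5.1 has two sets of BLQ rules.

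- **Individual plots and PK parameter calculation.** For BLQ before the first measurable concentration of a profile, "it is assigned as zero for Day 1 and as LLOQ for Day 29". For the rest, "If BLQ values occur between measurable concentrations or after the last measurable concentration, it is treated as missing".
- **Mean plot and concentration summary.** "BLQ will be set as zero", and then "The only exception is that the pre-dose BLQ on Day 29 will be set as LLOQ". "Mean concentration at any individual time point are only calculated if at least half (50%) of the patients have valid values", where valid means measurable and not missing. This condition appears only in this second set.

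Missing pre-dose samples have their own rule. "In cases of missing pre-dose values on Day 1, the missing components will be assumed as zero". For Day 29, "the individual minimum observed concentration during the dosing interval will be used as pre-dose concentration values". Other missing values are not imputed.

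SAP 2.3.3.2 names Ctrough as one of four PK parameters to be calculated where possible, defines it as the "concentration observed at pre-dose", and restricts it to Day 29. SAP 3.5.3 summarizes the parameters descriptively, examines fold-increase in exposure between dose cohorts where data suffice, and allows a dose-proportionality analysis.

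**The concern.** Ctrough is reported at one time point only, so no later trough can correct it. A value below LLOQ that is recorded as LLOQ is always overstated, and the SAP gives no reason for treating Day 29 pre-dose differently from other visits in the same table or plot. A missing trough filled with another sample's concentration may be summarized as though it had been observed, which conflicts with the definition of the parameter.

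What is at stake is modest: the reported Day 29 trough, the shape of the mean profile between Days 22 and 29, and any comparison of troughs between arms. Protocol 1.8 says the PK data will help establish doses for later development, so a trough that is an artefact of the convention should be visible as such.

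**Working it through.** **Inputs from the documents.** Doses on Days 1 and 29 (Protocol 3.1). PK samples pre-dose, 3 h and 8 h on dosing days, and at each visit, so Days 8, 15 and 22 lie between the doses (SAP 3.5, Protocol Appendix A). Twelve patients per active arm (SAP 2.2.4). LLOQ, BLQ share, half-life, between-patient CV and the rate of missing samples are not given, so every size below rests on a labelled assumption. The plan has no figure of its own to reproduce.

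**1. The same BLQ result under each rule set**

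| Sample | Summary and mean plot | Parameter calculation |
|---|---|---|
| Day 1 pre-dose | 0 | 0 |
| Day 22, between or after measurable values | 0 | missing |
| Day 29 pre-dose, leading the second-dose profile | LLOQ | LLOQ |

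The zero-to-LLOQ contrast therefore exists in the summary and mean plot, not in parameter calculation. If k of 12 patients are BLQ on both days, those patients alone raise the arm mean by k/12 × LLOQ: 0.25 × LLOQ for k = 3, and 0.50 × LLOQ for k = 6, the most that the 50% rule allows.

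**2. Arm wholly BLQ before the second dose, measurable after it.** Each Ctrough is LLOQ, so the mean is 12 × LLOQ / 12 = LLOQ, with SD 0. The concentration summary would leave that mean blank, because 0% is below 50%. No such limit is stated for the parameter summary.

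**3. Error against a true mean.** Assume a lognormal trough X in LLOQ units with P(X < 1) = f, σ² = ln(1 + CV²), and CV 30% to 100%. LLOQ and zero substitution differ by exactly f × LLOQ. Simulated errors:

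| BLQ share f | BLQ as LLOQ | BLQ as zero |
|---|---|---|
| 10% | +0.7 to +0.9% | −1.7 to −5.7% |
| 25% | +3.0 to +3.8% | −6.6 to −16.6% |
| 50% | +9.4 to +15.1% | −20.3 to −38.4% |
| 75% | +22.7 to +49.4% | −43.8 to −64.7% |
| 90% | +41.7 to +117.5% | −67.2 to −83.8% |

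With n = 12, the 50% rule lets a summary mean be reported with binomial probability P(at least 6 measurable) = 0.99, 0.61 and 0.05 at f = 25%, 50% and 75%. The last two rows therefore matter mainly for the Ctrough parameter summary.

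**4. A single scenario.** Half the arm is BLQ and the measurable values average 2 × LLOQ.

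- BLQ as LLOQ: 0.5 × 1 + 0.5 × 2 = 1.5
- BLQ as zero: 0 + 0.5 × 2 = 1.0
- Lognormal with median at LLOQ: 2·exp(σ²/2)·Φ(σ) = 2 gives σ ≈ 0.73, so the true mean is exp(σ²/2) ≈ 1.30

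The errors are 1.5/1.30 − 1 = +15% for LLOQ and 1.0/1.30 − 1 = −23% for zero.

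**5. Missing Day 29 pre-dose value.** Assume mono-exponential decline. The SAP leaves at least three readings open.

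- *Days 1 to 29, post-dose samples only.* Day 22 stands in, at 2^(7/t½) times the true trough: 2.00, 1.41, 1.19 and 1.09 for t½ of 7, 14, 28 and 56 days. With 10% to 30% residual CV, the expected minimum of Days 8, 15 and 22 over the true trough is 1.98–2.00, 1.33–1.41, 1.04–1.18 and 0.90–1.06.
- *Day 1 pre-dose zero included.* The minimum is 0, so the fill-in is too low.
- *Interval starting on Day 29.* The minimum is a later sample. For equal doses, Day 57 over Day 29 is 1 + 2^(−28/t½) = 1.06, 1.25 and 1.50 for t½ of 7, 14 and 28 days.

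The SAP also does not say whether a BLQ sample enters the minimum as zero, as LLOQ or not at all.

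**The case against.** The strongest reply is that LLOQ substitution is less wrong than the zero used elsewhere. Over the CVs and BLQ shares up to 50% examined above, that is correct, and it stands. A reader might infer that the Day 29 mean is overstated by 50%, from 1.5 against 1.0. That ratio compares two conventions, not a convention with the truth, and most of the gap is the error of zero.

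It can also be said that the missing-value rule is meant only for non-compartmental work: its paragraph opens in those terms, and missing values are excluded from summary means. This is a fair reading for the concentration summary. It does not settle Ctrough, which SAP 2.3.3.2 and 3.5.3 place among the non-compartmental parameters. Nothing limits the fill-in to anchoring the second-dose AUC.

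Finally, the reach is small. These parameters are exploratory, individual concentrations are listed (SAP 3.5.2), and the stated PK objective is the population model, which these rules do not govern. That also stands, and it keeps this a minor point.

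**Conclusion.** The point holds, at low severity. For BLQ the direction is certain: each Day 29 pre-dose BLQ is overstated, and the mean rises by at most f × LLOQ. The inconsistency between visits is real in the summary and mean plot. For missing values the defect is that the rule is undefined and may present an imputed number as an observed trough.

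A reader might go further and infer that both rules bias the trough upward. The documents do not support that for the missing-value rule, because the interval is not named and the result can be high, about right or low. A reader might also infer that lower-dose arms suffer most. That is plausible, but no BLQ frequencies are given by dose.

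The percentages above depend on assumed lognormal troughs, CVs, BLQ shares and half-lives. If few Day 29 samples are BLQ or missing, the effect is negligible. The primary safety endpoints and the PCSK9 and LDL-C endpoints are untouched. The second-dose AUC is affected only marginally, through its pre-dose anchor.

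**What to change.** Amend SAP 3.5.1 as follows.

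1. Leave a missing Day 29 pre-dose value missing for Ctrough and the concentration summary. If a fill-in is kept to anchor the second-dose AUC, name the interval, exclude the Day 1 pre-dose zero, and say how BLQ counts in the minimum.
2. List a BLQ Day 29 trough as BLQ and give n (%) BLQ per arm.
3. Use one BLQ convention across visits in the mean plot and concentration summary.
4. Show mean Ctrough with BLQ as zero and as LLOQ, as bounds, or give a censored-data estimate. Zero alone is not enough, because it is biased downward.

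The cost is a few sentences and one extra summary row. A few trough values become missing, and no new data are needed.
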